### 8.2. Key Definitions

- Age will be collected in the eCRF and the derivation is defined as follows:  
Age = year of informed consent – year of birth
- BMI will be calculated using weight at baseline and height at screening using the formula below:  
$$\text{BMI (kg/m}^2\text{)} = \text{weight (kg)} / [\text{height (m)}]^2$$
- Baseline

Baseline is defined as the last non-missing assessment before the date/time of first dose of any study drug and includes assessments taken on Day 1, unless otherwise specified.

For PK analysis, the baseline values are those collected predose at all scheduled visits per Schedule of Assessments in [Table 1](#).

- Change from baseline

The change from baseline will be calculated for each post-baseline assessment as:

Change from baseline = Post-baseline value – baseline value

- Percent change from baseline

The percent change from baseline will be calculated for each post-baseline assessments as:

Percent change from baseline =

$$(\text{Post-baseline value} - \text{baseline value}) * 100 / \text{baseline value}$$

### 8.3. Missing Data

For the purposes of assessing treatment emergence for AEs or classifying medications into prior/concomitant, the following algorithms will be used for partially missing dates. However, the assessment times (start date, stop date) without imputation will be presented in the listings.

For start dates of events:

This document is confidential.

- Only the year is reported:
  - If the participant did not receive any study drug (i.e., study intervention start date is missing), then start date will be set to 'January 1'
  - If the participant received the study drug (i.e., study intervention start date is not missing):
    - If the year of the start date is identical to that of the study intervention start date and the stop date contains a full date and earlier than the study intervention start date, then start date will be set to 'January 1', otherwise the start date will be set to the study intervention start date.
    - If the year of the start date is not identical to that of the study intervention start date, then the start date will be set to 'January 1'.
- Only the month and year are reported:
  - If the participant did not receive any study drug, then the start date will be set to the 1st day of the month.
  - If the participant received any study drug:
    - If the month and year are identical to the month and year of the study intervention start date, and the stop date contains a full date earlier than the study intervention start date, then the start date is set to the 1st day of the month, otherwise set start date to the study intervention start date.
    - If the month and year are not identical to the month and year of the study intervention start date, the start date will be set to the 1st day of the month.

For stop dates of events:

- Only the year is reported: if the last visit is in the reported year, the date of last visit will be used as the stop date; otherwise, '31 December' will be used as the stop date.
- Only the month and year are reported: if the last visit is in the reported month and year, the date of last visit will be used as the stop date; otherwise, the last day of the reported month and year will be used as the stop date.

If an AE has the start date completely missing, this AE will be considered as treatment-emergent, unless the stop date is before first dose of randomized study drug.

If a medication has the stop date completely missing, this medication will be considered as ongoing and concomitant.

There is no imputation for missing values in the safety analysis. The imputation of efficacy data is described in [Section 10](#).

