#### 9.5. Prior and Concomitant Medications and Procedures

Medications will be coded using the World Health Organization (WHO) Drug Dictionary Version September 2021 or later, and subject incidence will be tabulated by Anatomic Therapeutic Class (ATC) Level 2 and preferred term (PT) for the Safety Analysis Set. The systemic medication of psoriasis will be summarized and listed separately.

Prior procedures will be collected with medical history, coded using MedDRA Version 24.1 or later and summarized by SOC and PT for the Safety Analysis Set.

This document is confidential.

See [Section 8.3](#) for handling of partial dates for medications/procedures, in the case where it is not possible to define a medication/procedures as prior, concomitant, or post treatment.

- Prior medications/procedures are the medications/procedures which started and stopped prior to the first dose of study drug.
- Concomitant medications/procedures are medications/procedures which started prior to, on or after the first dose of study drug and before or on the date of last dose of study drug.
- Post medications/procedures are medications/procedures which started after the last dose of study drug.

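### SAP 8.3: a record with a year-only start in the first-dose year and a month-and-year stop in an earlier month gets a start date after its own stop date (minor)

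*SAP*

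**What the plan says.** SAP 8.3 opens with an unconditional scope: "For the purposes of assessing treatment emergence for AEs or classifying medications into prior/concomitant, the following algorithms will be used for partially missing dates". Listings keep the dates as reported.

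For a dosed subject whose start is known only by year, and whose start year is the first-dose year, the start is 1 January if "the stop date contains a full date and earlier than the study intervention start date"; "otherwise the start date will be set to the study intervention start date". The branch for a start known by month and year has the same full-date condition ("and the stop date contains a full date earlier than the study intervention start date").

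Stop dates are imputed separately. For a month-and-year stop, the last visit date is used if it falls in that month; "otherwise, the last day of the reported month and year will be used as the stop date". The section gives no order for the two imputations and does not compare their results.

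For an AE with no start date at all, "this AE will be considered as treatment-emergent, unless the stop date is before first dose of randomized study drug". That rule has no full-date condition.

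SAP 9.5 gives the classification: "Prior medications/procedures are the medications/procedures which started and stopped prior to the first dose of study drug". Its concomitant definition tests the start date only. Just before these definitions, 9.5 refers to 8.3 for medications and procedures whose status cannot otherwise be determined, which is narrower than the opening of 8.3.

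**The concern.** The full-date condition discards information that settles the question. A stop in a calendar month wholly before first dose shows that the record ended before dosing, whatever the day. The rule nevertheless sends it to the default and gives it a start on the first-dose date, while the stop rule in the same section places its end earlier.

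The section is also uneven. An AE with no start date and an earlier month-and-year stop is not treatment-emergent. Add the start year and the same AE becomes treatment-emergent, so more information gives a worse answer.

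At stake are the prior and concomitant medication tables (14.1.4.1.1 and 14.1.4.1.2), possibly the matching procedure tables (14.1.4.2.1 and 14.1.4.2.2), and the TEAE tables, including the Day 1 to 3 onset category in SAP 13.1.4.

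**Working it through.** The plan states no figure to reproduce. The check applies the rules of SAP 8.3 literally.

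Inputs: the start and stop rules above; AE collection from consent (SAP 13.1); a 28-day Screening Period (SAP 4.1). The documents give no actual first-dose dates, so 15 Jul 2022 is an assumption, with the last visit on Day 141 (2 Dec 2022).

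| Start | Stop | Imputed start | Imputed stop | Order |
|---|---|---|---|---|
| 2022 | 20 Mar 2022 | 1 Jan 2022 | 20 Mar 2022 | valid |
| 2022 | Mar 2022 | 15 Jul 2022 | 31 Mar 2022 | start 106 days after stop |
| 2022 | Jun 2022 | 15 Jul 2022 | 30 Jun 2022 | start 15 days after stop |
| 2022 | Jul 2022 | 15 Jul 2022 | 31 Jul 2022 | valid |
| 2022 | 2022 | 15 Jul 2022 | 2 Dec 2022 | valid |
| 2021 | Mar 2022 | 1 Jan 2021 | 31 Mar 2022 | valid |
| Jul 2022 | Jul 2022 | 15 Jul 2022 | 31 Jul 2022 | valid |

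The 106 days are 30 (April) + 31 (May) + 30 (June) + 15 (July).

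**Extent.** For a first dose in month *m* there are *m* − 1 earlier months in the same year. Summing (days in month) × (*m* − 1) over a 365-day year gives 28 + 62 + 90 + 124 + 150 + 186 + 217 + 240 + 279 + 300 + 341 = 2,017 pairings of a first-dose date with an earlier stop month. All 2,017 put the start after the stop. The smallest gap is 1 day (first dose on the first of a month, stop in the month before). The largest is 365 − 31 = 334 days (first dose 31 December, stop in January). These are possible date combinations, not expected records.

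**Month-and-year start.** The full-date condition applies only when the start month is the first-dose month. A partial stop then cannot be known to precede first dose, so the condition does no harm there. Running all partial-date combinations gave one other inverted group: 718 pairings of a month-and-year start with a year-only stop. In each, the start month falls after the month of the last visit. That is a separate and unlikely situation, not this defect.

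**AEs.** With first dose on 15 Jul, Day −28 is 17 Jun. An AE recorded as start 2022, stop Jun 2022 (third row) becomes a TEAE with onset on Day 1. With no start date, the same stop makes it non-treatment-emergent.

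**Medications.** In the second row the imputed start is not before first dose, so the record fails the 9.5 definition of prior. It meets the concomitant definition, because that looks only at the start.

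**The case against.** The strongest reply is the reference in SAP 9.5. It invokes 8.3 only where status cannot be determined, and a medication that stopped in March plainly started and stopped before July. On that reading no imputation is needed and it stays prior. This stands in part: it is why one cannot say that every such medication is misclassified. But 8.3 itself is unconditional for medications, so the two sections conflict and the program could follow either. Procedures are not named in the opening of 8.3 and reach it only through 9.5, so for them the narrower reading is the stronger.

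SAP 13.1.1 counts an AE as treatment-emergent when its status is unclear, which could be called deliberate caution. But an AE with a stop in an earlier month is not unclear, and 8.3 accepts such a stop when the start is wholly missing.

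Stop dates might be meant to be imputed first and then count as full. The problem would vanish, but the SAP states no such order and the full-date wording would then exclude no partial stop date.

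A reader might infer three stronger things that the documents do not support:

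- *An AE that ended months before first dose becomes a TEAE.* AEs are collected from consent and Screening lasts 28 days, so only an AE that ended in the calendar month before first dose is exposed.
- *Washed-out psoriasis therapy appears as prohibited treatment begun on Day 1 and distorts the per protocol set.* Medication tables are by drug class and preferred term, without start dates. Deviations are recorded by the site monitor and reviewed at the blind data review meeting (SAP 6.8, 9.2). Listings show reported dates, and prior systemic psoriasis therapy has its own page and table (SAP 9.6, Table 14.1.4.3).
- *The washouts imply many affected subjects.* A washout constrains the stop date, but the rule is triggered by the start year. With a 24-week washout (168 days), start and stop both fall in the first-dose year only if first dose is about 18 June or later.

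**Conclusion.** The point holds as a minor specification error in one branch of SAP 8.3. On the literal text, a year-only start in the first-dose year with a month-and-year stop in an earlier month always gives a start after the stop, by 1 to 334 days depending on the dates.

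The consequences are limited. A screening AE that ended in the calendar month before first dose would be called a TEAE. A finished medication, and less clearly a procedure, would move from prior to concomitant if the wording of 8.3 is followed over that of 9.5.

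The documents do not allow a count of affected records. It is probably small: the start must be year-only, the stop must lack a day, and both must fall in the first-dose year, while Protocol 9.6.1 asks for dates of use. PASI-75, membership of the per protocol set and the deviation review do not depend on this rule. The conclusion assumes that the text is programmed as written, without first imputing stop dates.

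**What to change.** In the year-only branch of SAP 8.3, replace the full-date condition with: *the stop date, after stop-date imputation, is earlier than the study intervention start date*. Add one sentence: *an imputed start date is never later than the imputed stop date*. The month-and-year branch may be reworded to match, for consistency only. SAP 9.5 and the opening of 8.3 should also be aligned on whether imputation applies to every partial date or only where status is undetermined.

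Under this change the second row above becomes 1 Jan to 31 Mar 2022 (prior), and the third becomes 1 Jan to 30 Jun 2022 (not treatment-emergent). The cautious default is kept: a stop in the first-dose month, or a year-only stop in the first-dose year, still imputes to first dose or later, so the start stays at first dose. The cost is a few lines of SAP text and of the derivation program, with no new data.

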#### 8.4. Visit Windows

The visits recorded in database will be used for all analyses. There is no plan to re-assign visits based on actual visit dates.

This document is confidential.

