	
Follow-up Period assessments will be performed on Day 141.
 
After the Screening Period, approximately 125 eligible subjects with a confirmed diagnosis of psoriatic plaques, a BSA involvement of $\geq 10\%$ (at Screening and Baseline), a PASI score 12 to 40 (at Screening and Baseline), and an sPGA ≥ 3 (at Screening and Baseline) will be randomly assigned to receive ME3183 [] mg twice daily [BID], [] mg once daily [QD], [] mg BID, or [] mg QD) or placebo in a 1:1:1:1 ratio. To promote balanced allocation, randomization will be stratified by the subject's receipt (yes/no) of previous treatment with a biologic drug for psoriasis. Bio-naïve subjects will be randomized above 50% of the planned total subject randomization.
 
After randomization (Day 1), all subjects will be evaluated at Baseline and at Weeks 1, 2, 4, 8, 12, 16, and 20. Efficacy assessments (ie, PASI, BSA, sPGA, and PRO assessments [DLQI and the itch NRS]), will be assessed at Baseline (Day 1) and at Weeks 1, 2, 4, 8, 12, 16, and 20. Blood samples for PK assessment will be collected predose at Weeks 1, 4, 8 and 16. Blood samples for [] assessments will be collected predose at Baseline (Day 1), Weeks 4 and 16. Safety and tolerability will be assessed by physical exam, monitoring for AEs and serious AE (SAEs), demographics, medical history, vital signs and safety laboratory tests (hematology, coagulation, blood chemistry, and urinalysis) at Baseline (Day 1) and Weeks 1, 2, 4, 8, 12, 16, and 20. ECGs will be assessed at Baseline (Day 1) and Weeks 4, 8, 12, 16, and 20.

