7.2 Discussion of Study Design

A double-blind, randomized, placebo-controlled study is considered a gold-standard for conducting any interventional study. This design will minimize bias and provide reference data (ie, data from placebo treatment group) for comparison of the efficacy and safety parameters of the ME3183.

Psoriasis is a chronic immune-mediated inflammatory disorder, which requires a chronic therapy. Primary efficacy assessments of psoriasis clinical studies are usually performed at 12 or 16 weeks after initiation of study treatment. This is therefore considered an acceptable treatment duration to observe a CS response that allows for discriminating among different tested doses of ME3183. Primary evaluations of apremilast, the only PDE4 inhibitor currently approved for psoriasis treatment, were also conducted at week 16. A 16-week Treatment Period was also deemed acceptable for the placebo arm because psoriasis is not a life-threatening disease; in case of unbearable flares, subjects can discontinue early from the study and receive appropriate treatment.

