Efficacy Assessments									
PASI score	X	X o	X	X	X	X	X	X	X
BSA	X	X o	X	X	X	X	X	X	X
sPGA	X	X o	X	X	X	X	X	X	X
PRO assessments	Itch NRS	-	X	X	X	X	X	X	X
	DLQI	-	X	X	X	X	X	X	X
CCI									
Other Assessments									

This document is confidential.

Study Procedures	Screening Period	Treatment Period							Follow-up Period b
		Visit 2	Visit 3	Visit 4	Visit 5	Visit 6	Visit 7	Visit 8 a	
	Screening (Visit 1)	Visit 2	Visit 3	Visit 4	Visit 5	Visit 6	Visit 7	Visit 8 a	Follow-up Visit (Visit 9)
	Week -4	Week 0	Week 1	Week 2	Week 4	Week 8	Week 12	Week 16	Week 20
	Days -28 to -1	Day 1 (Baseline)	Day 8 ( $\pm 1$ day)	Day 15 ( $\pm 1$ day)	Day 29 ( $\pm 3$ days)	Day 57 ( $\pm 3$ days)	Day 85 ( $\pm 3$ days)	Day 113* ( $\pm 3$ days)	Day 141** ( $\pm 3$ days)
Medical photography (target skin lesion) d	-	X	-	X	X	-	-	X	-
Clinical Drug Supplies									
Subject randomization	-	X	-	-	-	-	-	-	-
Dispense study drug	-	X	X	X	X	X	X	-	-
Administration of study drug g	-	X	X	X	X	X	X	-	-
Subject to return back unused study treatment for compliance check	-	-	X	X	X	X	X	X	-
Schedule the date/time for the next visit	X	X	X	X	X	X	X	X	-
Discharge the subject from the study site e	X	X	X	X	X	X	X	X	X

Abbreviations:  $\beta$ -hCG =  $\beta$ -human chorionic gonadotropin; AE = adverse event; BMI = body mass index; BSA = body surface area; C-SSRS = Columbia-Suicide Severity Rating Scale; DLQI = Dermatology Life Quality Index; ECG = electrocardiogram; FSH = follicle-stimulating hormone; HBV = hepatitis B virus; HCV = hepatitis C virus; PASI=Psoriasis Area and Severity Index; CCI [REDACTED]; PK=pharmacokinetic; PRO=patient-reported outcome; QTcF = QT interval corrected using Fridericia's formula; SAE = serious adverse event; sPGA = Static Physicians Global Assessment; WOCBP = women of childbearing potential; NRS = numerical rating scale.

\* The duration of the Treatment Period is from Day 1 to Day 112 and the end of Treatment Period assessments will be performed on Day 113.

\*\* The duration of the Follow-up Period is from Day 114 to Day 141 and the end of Follow-up Period assessments will be performed on Day 141.

a or Early Termination Visit.

b Subjects who discontinued or withdrew early from study treatment should return after 4 weeks of last dose of study treatment for follow-up safety assessments.

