### 7.2. Estimands for Secondary Efficacy Endpoints

The estimands for secondary efficacy endpoints are defined as below:

- Population: Subjects with moderate to severe plaque psoriasis defined by the study inclusion/exclusion criteria in [Section 4.2](#). The analysis population for the secondary efficacy endpoints will be full analysis set as defined in [Section 6.2](#).
- Variables:
  - Continuous variables measuring the percent changes from baseline in PASI score at all visits from Week 1 to Week 16
  - Binary variables indicating whether the subject has achieved  $\geq 50\%$ ,  $75\%$ ,  $90\%$  and  $100\%$  reduction from baseline in the PASI score at all visits from Week 1 to Week 16
  - Time to event variable measuring the time from baseline to the time achieving  $\geq 50\%$  and  $75\%$  reduction in PASI score in days respectively, censored by the date of last PASI assessment date for subjects who never achieves  $\geq 50\%$  or  $75\%$  reduction
  - Binary variables indicating whether the subject has achieved a sPGA score of "0" ("clear") or "1" ("almost clear") combined with a 2-point reduction on the 5-point sPGA scale at all visits from Week 1 and Week 16
  - Continuous variables measuring the changes from baseline in BSA at all visits from Week 1 to Week 16
  - Continuous variables measuring the changes from baseline in NRS at all visits from Week 1 to Week 16
  - Continuous variables measuring the changes from baseline in DLQI score at all visits from Week 1 to Week 16

This document is confidential.

- Binary variables indicating whether a subject achieves at least a 5-point reduction from baseline in the DLQI score at all visits from Week 1 to Week 16
- Population-level summary:
  - Binary variables will be summarized using numbers and proportions of subjects achieving that outcome of interest, then differences in the proportions between each ME3183 treatment group and placebo group will be calculated.
  - Continuous variables will be summarized using descriptive statistics by treatment group and overall. Mixed-effect model for repeated measures will be used to estimate the least-square (LS) mean differences between each ME3183 treatment group and placebo group.
  - Time to event variables will be summarized using medians and 95% CIs, Kaplan-Meier estimates, and hazard ratios estimated Cox proportional hazard models.
- Intercurrent events:

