  - Withdrawals or early terminations will be handled via while-on-treatment policy, where no missing data will be imputed, except for analyses listed below where intercurrent events will be handled via hypothetical strategy and missing data will be imputed using LOCF and NRI methods in addition to complete case analysis: percent change from baseline for PASI scores at all visits from Week 1 to Week 16, the numbers and percentages of subjects achieving  $\geq 50\%$ , 75%, 90% and 100% reduction from baseline in the PASI score at all visits from Week 1 to Week 16, the numbers and percentages of subjects achieving an sPGA score of "0" ("clear") or "1" ("almost clear") and a 2-point reduction from baseline.

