Descriptive statistics for the continuous secondary endpoints described above will be provided at each schedule visit by treatment group. Additionally, the secondary continuous efficacy endpoints (including percent changes for PASI, changes for DLQI, BSA and NRS) will be analyzed using a mixed-effect model for repeated measures (MMRM) with the change or percent change from baseline as the response variable, treatment group, visit, treatment-by-visit interaction as fixed effects, and the baseline value as a covariate. An unstructured covariance matrix will be used to model the correlation among repeated measurements. The Kenward-Roger adjustment will be used with restricted maximum likelihood (REML) to make proper statistical inference. The LS mean differences between ME3183 treatment groups and placebo at each scheduled visits along with the 2-sided 95% CIs and 2-sided p-values will be estimated from the MMRM model. In the event that MMRM with unstructured covariance matrix fails to converge, alternative covariance structures will be explored, including Toeplitz, heterogeneous Toeplitz, variance components, compound symmetry, heterogeneous compound symmetry, autoregressive and heterogeneous autoregressive covariance matrices, where the optimal covariance matrix structure will be selected based on Akaike's Information Criteria (AIC), where smaller values of AIC indicate better overall fit. MMRMs will be estimated for the secondary continuous efficacy endpoints using complete case analysis only.

Kaplan-Meier method will be used for summarizing the time to the first response of PASI-50 and PASI-75 in days. The time to the first response of PASI-50 and PASI-75 is defined as the number of days from the first dose of the study drug to the first response. If a subject does not achieve PASI-50 and PASI-75, the variable will be censored on the last PASI assessment date. Median time to response and 95% CI will be provided, when estimable. The CI will be based on log-log transformation. The reverse Kaplan-Meier plots of PASI-50 and PASI-75 will be presented by treatment group. The comparison of the time to PASI-50 and PASI-75 between each ME3183 treatment group and placebo will be performed using the log-rank test.

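### Time to PASI-50 and PASI-75 has no end-of-treatment cut-off, so a first response scored after study drug has stopped can count as an event

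*SAP*

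**What the plan says.** SAP 10.2 states that time to first PASI-50 or PASI-75 response "is defined as the number of days from the first dose of the study drug to the first response", and that without a response "the variable will be censored on the last PASI assessment date". SAP 7.2 starts the clock at baseline instead of first dose, on which nothing here turns, and censors the same way: "censored by the date of last PASI assessment date for subjects who never achieves". Neither section names Week 16 or the last dose as a limit. In SAP 5.2 every other secondary efficacy endpoint is restricted to Weeks 1 to 16; time to response is not.

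The Protocol synopsis says that PASI and the other efficacy measures "will be assessed at Baseline (Day 1) and at Weeks 1, 2, 4, 8, 12, 16, and 20". Dosing ends on Day 112 (Protocol 9.2) and the follow-up visit is on Day 141.

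For the secondary efficacy endpoints SAP 7.2 says: "Withdrawals or early terminations will be handled via while-on-treatment policy". Its exceptions are percent change in PASI, the PASI response proportions and the sPGA response. Time to response is not among them.

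On visits, SAP 8.4 says: "The visits recorded in database will be used for all analyses. There is no plan to re-assign visits based on actual visit dates". In SAP Table 1 the Visit 8 (Week 16) column carries the footnote "or Early Termination Visit".

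**The concern.** A literal programming of SAP 10.2 takes the earliest PASI score that meets the threshold, including one obtained after study drug has stopped. That response would be credited to the assigned arm in the Kaplan-Meier curves, the log-rank test and the hazard ratio. For a subject who withdrew, this is what a while-on-treatment strategy is meant to exclude. Protocol 7.2 adds that in case of unbearable flares "subjects can discontinue early from the study and receive appropriate treatment", so such a score may also reflect another therapy.

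A second question follows from the same silence about post-exit scores. Early termination shares the Week 16 column, and SAP 8.4 keeps the recorded visit label. If the database stores an exit visit as Visit 8, its PASI would enter the primary analysis as an observed Week 16 value. Complete case, LOCF and NRI would then treat that subject identically. This part depends on a label the documents do not give.

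**Working it through.** The plan states no figure for this endpoint, so there is nothing to reproduce. The check has three steps.

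**1. Is the follow-up score off drug?** Day 141 - Day 112 = 29 days. Protocol 5.2.2 gives a half-life of about 16 to 24 hours after single doses in healthy adults. 29 x 24/24 = 29 half-lives; 29 x 24/16 = 43.5. Yes.

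**2. Do the rules exclude it?**
- Event: first response, no end date (SAP 10.2).
- Censoring: last PASI date (SAP 7.2 and 10.2), not last dose or Week 16.
- Intercurrent-event policy: while-on-treatment for withdrawals (SAP 7.2), with no exception for this endpoint.
- Visit rule: recorded labels are kept (SAP 8.4), with no on-treatment restriction.

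Nothing excludes it. For withdrawals, the event and censoring rules and the policy disagree. For completers, no rule speaks.

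**3. How much could one such score matter?** From the documents: 25 per arm and 10% drop-out, so 25 x 0.10 = 2.5 exits per arm (2 used). Assumed: active first PASI-75 responses 1, 2, 2, 3 on Days 29, 57, 85, 113; placebo 1, 1 on Days 85, 113; exits on Day 57; all others censored on Day 113. The log-rank statistic is (O - E)^2/V for the active arm, where at each event day E = d x n1/n and V = d(n1/n)(1 - n1/n)(n - d)/(n - 1).

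Base case, exits censored on Day 57:

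| Day | At risk, active/placebo | Events, active/placebo | E | V |
|---|---|---|---|---|
| 29 | 25/25 | 1/0 | 0.500 | 0.250 |
| 57 | 24/25 | 2/0 | 0.980 | 0.489 |
| 85 | 20/23 | 2/1 | 1.395 | 0.711 |
| 113 | 18/22 | 3/1 | 1.800 | 0.914 |

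O = 8, E = 4.675, V = 2.364, chi-square 4.677, two-sided p = 0.031; Cox hazard ratio (Efron ties) 4.71 (1.00 to 22.18).

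Now follow the exits to Day 57 + 29 = Day 86 and let one respond there. Day 85 becomes 22/25 at risk (E 1.404, V 0.715). Day 86 adds 20/24 at risk with one event (E 0.455, V 0.248). Totals: E = 5.138, V = 2.616.
- Placebo response: O = 8, chi-square 3.131, p = 0.077, hazard ratio 3.13 (0.83 to 11.81).
- Active response: O = 9, chi-square 5.701, p = 0.017, hazard ratio 5.28 (1.14 to 24.48).

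Completers: moving their censoring from Day 113 to Day 141 with no new response changes nothing. One first response on Day 141 gives p = 0.072 (placebo) or 0.016 (active). The problem is therefore added events, not longer follow-up.

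**Conditional Week 16 illustration** (one-stratum Mantel-Haenszel, one-sided; applies only if exits are stored as Visit 8). With 2 exits per arm, NRI gives 7/25 v 2/25, p = 0.034. If one active exit met PASI-75 at exit, all three analyses give 8/25 v 2/25, p = 0.018. If instead NRI gives 8/25 v 2/25 (p = 0.018) and one placebo exit met it, all three give 8/25 v 3/25, p = 0.046. The planned level is 0.025. SAP 10.1 also stratifies by prior biologic use, which this ignores.

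**The case against.** The SAP does give an event rule and a consistent censoring rule, and it glosses while-on-treatment as meaning that missing data are not imputed. On that narrow gloss there is no conflict. The gloss covers missing data, however; it does not say that post-treatment scores count, and the strategy's name says they should not.

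For withdrawals the route is also narrow: the subject must return, have PASI scored and respond for the first time about four weeks off drug. Protocol 7.4 asks early stoppers for the Day 141 assessments, but Table 1 footnote b describes that visit as safety follow-up, so the score may not exist. The calculations use assumed counts, and with ten events any single addition moves the p-value. All of this stands: they show sensitivity, not likelihood.

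Four stronger readings are tempting, and the documents do not support them.
- **SAP 7.2 is breached for everyone.** Its policy names withdrawals and early terminations; completers' Week 20 scores are not covered.
- **The primary endpoint is shown to be contaminated by exit scores.** The footnote and Protocol 7.4 say what to assess at exit, not how to label it. SAP 2.2 separates completing Visit 8 from terminating early, and SAP 7.1 applies LOCF and NRI to withdrawals, which presupposes no Week 16 value. Subjects who leave for worsening disease are also unlikely exit responders.
- **LOCF would carry the follow-up score back to Week 16.** By recorded label that score belongs to Week 20, after the visit being filled.
- **Off-drug responses would reflect other therapy.** Protocol 7.2 and 8.4 allow other treatment, but Appendix 2 restricts most psoriasis therapies until four weeks after the last dose. It is a possibility only.

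**Conclusion.** The point holds for time to PASI-50/75. Applied literally, SAP 7.2 and 10.2 allow an off-drug score to count as a first response. This contradicts the SAP's own policy for withdrawals and leaves the cut-off undefined for completers. The effect is on a secondary endpoint in a proof-of-concept study with no formal sample size calculation. Its size is unknown. Under the assumed 8 v 2 responses, one extra event moves p from 0.031 to between 0.017 and 0.077, depending on the arm.

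The Week 16 labelling question is a safeguard, not a demonstrated defect. It matters only if exit visits are stored as Visit 8, but it then reaches the primary endpoint and removes the contrast between complete case, LOCF and NRI for those subjects. It should be answered from the database specification.

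**What to change.** - **SAP 7.2 and 10.2.** Count first responses and censor using only PASI scores from scheduled visits up to and including Week 16. State that the Day 113 assessment is included, since the last planned dose is Day 112. Admit an early-termination score only if it falls within a stated on-treatment limit from last dose; the team should set and justify that limit.
- **Exclude the post-treatment follow-up by visit type, not by date.** Its planned spacing is 29 +/- 3 days after last dose, or 26 to 32. A last dose between Day 110 - 32 = 78 and Day 116 - 26 = 90 can therefore place it inside the Week 16 window of Days 110 to 116.
- **SAP 8.4, conditional safeguard.** Confirm how exit visits are labelled. State that an early-termination PASI outside Day 113 +/- 3 is not an observed Week 16 value, so that LOCF and NRI apply to withdrawals as SAP 7.1 intends. Scheduled visits keep their recorded label; the window is needed only for exit visits, which have no scheduled day.
- **Reconcile Protocol 7.4 with Table 1 footnote b** on whether early stoppers have PASI scored at follow-up.

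Cost: a few sentences in SAP 7.2, 8.4 and 10.2 and one derivation flag in the efficacy dataset. No new data are needed. The rule should be fixed before treatment codes are applied, so that the choice cannot follow the results.
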